4.2 Analysis close date

The analysis closing date is September 2023 after all data has been checked and cleaned.

Data cleaning

The data will be checked to ensure that there are no erroneous entries and that all missing data is properly coded. Any change will be made on the source documents (if applicable) and updated in the database accordingly.

4.3 Data download

The database will be locked once that all trial data are complete and verified according to the Monitoring Plan. When locked, the data will be downloaded into .csv, and .dta formats for statistical analyses.

5. STATISTICAL ANALYSES

5.1 General considerations

5.1.1 Data summary

Unless otherwise specified, summaries for continuous variables will include the descriptive statistics for number of participants (n), mean, standard deviation (SD), minimum (min), median, and maximum (max). The min and max values will be presented to the same number of decimal places as the raw data. The means and medians will be presented to one more decimal place than the raw data. The SDs will be presented to two more decimal places than the raw data. If the raw data has 3 decimal places or more, 3 decimal places will be presented for mean, median, min and max, and SDs.

Summaries for categorical (discrete or dichotomous) variables will include the number and/or percentage of participants in a particular category. Percentages will be presented to one decimal place, unless otherwise specified. Population counts (either number of participants or number of time points at the assessment) for each treatment group will be used as the denominator in the calculation of percentages unless otherwise specified.

5.1.2 Baseline

Unless otherwise specified, the baseline will be defined as the last non-missing value prior to the first dose of study drug.

Change from baseline is defined as the difference between the post-baseline assessment value and the baseline value, i.e., Post-baseline Assessment Value – Baseline Value.

5.1.3 Study day

Study day is relative to the day of first dose of study drug. Day 1 is defined as the day of the first dose of study drug. Study days after Day 1 are calculated as: Assessment date – Date of Day 1 + 1. Study days prior to Day 1 are calculated as: Assessment date – Date of Day 1. The day prior to Day 1 is Day -1.

5.1.4 Unscheduled visits

Unscheduled visit value may be used to provide a measurement for a scheduled time point, a baseline, a last or a worst value, if appropriate according to their definitions. The unscheduled visit values will not be summarized by unscheduled visit but will be presented in the listings chronologically as the visit occurs.

5.1.5 Handling of missing data

Every effort will be made to minimise the amount of missing data in the trial. Information on the reason for missing data will be obtained, whenever possible.

Baseline demographic data

For missing data on age, gender, height and weight at baseline, multiple imputation will be performed. **Efficacy data**

For the efficacy analysis, the worst-case scenario will be considered, where participants with missing data will be considered as treatment failures. In such a case it will be assumed that all participants with no egg count data at day 21 will have the same egg count as at baseline.

Adverse Events

The following imputation rules for missing or partial AE start dates are used:

- If only Day is missing, the start day will be the first day of the month or the date of study drug first dose if the AE end date is on/after the date of study drug first dose or is missing/partial AND the start year and month of the AE are the same as year and month of the study drug first dose date;
- If Day and Month are both missing, the start date will be January 1 of the year or the date of study drug first dose if the AE end date is on/after the date of study drug first dose or is missing/partial AND the start year of the AE is the same as year of the study drug first dose date;
- If Day, Month, and Year are all missing, the date will not be imputed. However, if the AE end date is on/after the date of study drug first dose, then the AE will be considered a TEAE.

The missing or partial AE stop data will not be imputed.

If the severity of an AE is missing, it will be classified as "severe" in the summary tables by severity. If the assessment of relationship of study drug is missing, it will be classified as "related" to the study drug.

Concomitant Medications

The same imputation rule as AE start date imputation will be used for missing or partial start dates of medications.

The missing or partial medication stop data will not be imputed.

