#### **Rationale for Study Population Selection**

Participants between 5 and 18 years of age will be screened. This age range has been selected because of the high prevalence of STH in this population (it is the group most affected with STH), and the beneficial logistics implications of recruiting/enrolling at schools. The total number of participants to be screened depends on the prevalence rates of STH at the study site(s). A participant infected with a mixture of worms will be counted in the sample size for each worm that the participant is infected.

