**ALIVE Study** 

Table 2. Final sample size calculation taking into account 10% lost-to-follow-up

	Pha	ase II		PHASE III	PHASE II/III
		N total		N total	
		Phase		Phase	
Group	N	ll 	N	III 	N total
Trichuris trichiura					
ALB	23	26	93	103	129
FDCx1	45	50	178	198	248
FDCx3	45	50	178	198	248
Total	113	126	449	499	625
Strongyloides.					
stercoralis					
ALB			42	47	47
FDCx1			108	120	120
FDCx3			107	119	119
Total		0	257	286	286
Hookworm					
ALB			91	101	101
FDCx1			91	101	101
FDCx3			99	110	110
Total		0	281	312	312
TOTAL		126		1097	1223

<sup>1Calculated by inflating the sample size using considering 10% lost-to-follow-up

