3.5 Determination of sample size

Sample size was calculated based on available data from peer-review publications complemented with reasonable estimates of efficacy for those experimental groups that have not been previously tested. For these calculations, the efficacy of the control arm (Albendazole 400mg in a single dose), was obtained for *T. trichiura* and hookworms from a systematic review and meta-analysis where

temporary trends in efficacy (with the corresponding confidence intervals) were incorporated (Table 3)[4]. For the efficacy of the control arm against *S. stercoralis*, an alternative source was used [5], since the systematic review by *Moser et al* did not include this species; for that reason, a clinical trial that included an arm of Albendazole 400mg for 3 consecutive days was used, assuming a "best case scenario" for the efficacy of the control group; this estimated efficacy is also in the range of a systematic review assessing the efficacy of Albendazole at various (but not single) doses[5]. For the FDC at single dose, the calculations were based on the estimated efficacies (and their corresponding confidence intervals) in a systematic review that calculated the Relative Risks of cure of diverse drug regimens against Albendazole 400mg single dose (Table 3)[6,7]. For. *S. stercoralis*, the estimated efficacy of FDC was calculated based on a recent clinical trial using lvermectin single and multiple-dose regimens [8]. Finally, for the FDC in 3-dose regimens, considering its use in public health, deployment logistics in MDA campaigns and expected impact of the FDC, we estimated that an improvement of at least 15 percentage points would be the minimum improvement in efficacy to be demonstrated in order to make the FDCx3 regimen worth considering.

Sample size was calculated estimating the efficacy of the different experimental drug or combinations for each of the STH of interest [9,10], and gathering the individual samples sizes for the study. The sample size was calculated for pairwise comparisons of the expected Cure Rates for three study groups with an overall significance level of 5% adjusted for multiple tests by Bonferroni's correction, 80% power and inflated for 10% lost-to-follow-up.

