The estimated total number of participants for the adaptive design is 1223 (*T. trichiura* 625, *S. stercoralis* 286 and hookworm 312). This sample size is powered to be able to measure efficacy for all three species in the phase III component. The sample size for the phase II component is 20% of the total participants for *T. trichiura* (126 participants). The remaining 80% of the *T. trichiura* participants will be randomised in the phase III component. Table 4 details the stratification of the participants per species with a 10% lost-to-follow-up.

The total number of participants to be included in this clinical trial is 1223 (126 in phase II and 1097 in phase III). Following randomisation, 251 participants will be allocated to the ALB treatment arm, 427 will be allocated to the FDC treatment arm and 419 in the FDCx3 treatment arm. Table 4 details the stratification of the participants per species with a 10% lost-to-follow-up.

The 10% lost-to-follow-up inflated sample sizes of the ALB-group for *T. trichiura, S. stercoralis* and hookworm are 129, 47 and 101 respectively, and the corresponding sample sizes of the individual experimental treatment groups are 248, 120, and 101 for FDC-group and 248, 119 and 110 for FDCx3-group. The corresponding powers of each of the tests are 91%, 100% and 80% to compare the CRs of *T. trichiura* in ALB vs FDC, ALB vs FDCx3 and FDC vs FDCx3 respectively; 95%, 100% and 80% to compare the CRs of hookworm respectively for ALB vs FDCx3 and FDC vs FDCx3 comparisons. We do not compare CRs of hookworm in ALB and FDC as they are known to be the same. These powers were computed assuming that the expected CRs for *T. trichiura* are 23.7%, 43.7% and 59% in the ALB, FDC and FDCx3 groups respectively; 45%, 79% and 94% for *S. stercoralis* and 79.5%, 79.5% and 95% for hookworm. **Table 3** and **Table 4** show the sample size calculation according to the expected Cure Rate for each drug and helminth of interest, and the resulting sample size inflated by 10% due to the estimated lost-to-follow-up. Assumptions used for the sample size calculations (e.g. expected CRs, lost-to-follow-up, etc) should be checked during the interim analysis.

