4. ANALYSIS POPULATIONS

4.1 Study population data sets

Safety population

The safety analysis will be based on the intention-to-treat (ITT) population, defined as all participants who were randomized in the trial.

Efficacy population

The efficacy analysis will be based on the ITT population. For the handling of missing data, the worstcase scenario will be considered, considering all individuals without efficacy data as treatment failures. **Population PK analysis (phase II)** A complete description of the pk analysis can be found in the statistical analysis plan for pharmacokinetics.

For population pharmacokinetic analysis, the 126 participants included in the 3 arms of phase II (26 in arm 1, and 50 in the arms 2 and 3) will be randomly assigned to different subgroups (7 subgroups for arm 1, and 10 subgroups for arm 2 and 3) with different sampling times (2 blood samples per subgroup for arm 1 and 2, and 2 blood samples plus predose on Day 2 per subgroup for arm 3). The two sampling times has been randomly obtained from two different post-dosing ranges covering from 1 to 7 hours (range I) and from 8 to 72 hours (range II). Thus, the overall sampling times describes the entire pharmacokinetic profile for the two drugs (Ivermectin and Albendazole) for each of the 3 groups of body weight (Group 1: 23-30kg, Group 2: 30-45kg, and Group 3:15-23kg).

For the random assignment of the blood capilar extractions (with Mitra (40) Clamshell), a randomization of the times of PK extraction (9 points for arm 1 and 11 and 12 points for arms 2 and 3

respectively) will be carried out carried out for each arm of treatment: [+1h, +2h, +3h, +4h, +5h, +6h, +7h, +8h and +24h] for the arm 1 (albendazole treatment); and [+1h, +2h, +3h, +4h, +5h, +6h, +7h, +8h, +24h, +48h and +72h] for the arm 2 (coadministration IVM+Albendazole); and [baseline preadministration on Day 2 and +1h, +2h, +3h, +4h, +5h, +6h, +7h, +8h, +24h, +48h and +72h] for arm 3 (coadministration IVM+Albendazole)x3 consecutive days)..

For Arm 1 (albendazole treatment), the 9 points (+1h, +2h, +3h, +4h, +5h, +6h, +7h, +8h and +24h) has been divided in 2 groups:

i) One group of 5 points comprising the points from +1h until +5h

ii) One group of 4 points comprising the points from +6h until +24h

For assigning the 2 points we randomize 1 time from each group

For Arm 1 (5 subgroups of 4 participants + 2 subgroups of 3 participants):

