SubGroup 1 (n=4): +3h, +6h SubGroup 2 (n=4): +4h, +24h SubGroup 3 (n=4): +2h, +8h SubGroup 4 (n=4): +5h, +7h SubGroup 5 (n=4): +1h, +7h SubGroup 6 (n=3): +2h, +24h SubGroup 7 (n=3): +4h, +8h

For Arm 2 (albendazole + ivermectin treatment), the 11 points (+1h, +2h, +3h, +4h, +5h, +6h, +7h, +8h, +24h, +48h, +72h) has been divided in 2 groups:

i) One group of 6 points comprising the points from +1h until +6h

ii) One group of 5 points comprising the points from +7h until +72h

For assigning the 2 points we randomize 1 time from each group For Arm 2 (10 groups of 5 participants):

SubGroup 1 (n=5): +4h, +72h SubGroup 2 (n=5): +5h, +48h SubGroup 3 (n=5): +2h, +8h SubGroup 4 (n=5): +1h, +8h SubGroup 5 (n=5): +3h, +72h SubGroup 6 (n=5): +4h, +24h SubGroup 7 (n=5): +3h, +7h SubGroup 8 (n=5): +2h, +48h SubGroup 9 (n=5): +5h, +7h

For Arm 3 (10 groups of 5 participants), (albendazole + ivermectin treatment x 3 consecutive days), we follow the same schedules as for Arm 2, but adding predose on Day 2 and starting the extractions from that point, as follows

SubGroup 1 (n=5): predose Day 2, +4h, +72h SubGroup 2 (n=5): predose Day 2, +5h, +48h SubGroup 3 (n=5): predose Day 2, +2h, +8h SubGroup 4 (n=5): predose Day 2, +1h, +8h SubGroup 5 (n=5): predose Day 2, +3h, +72h SubGroup 6 (n=5): predose Day 2, +4h, +24h SubGroup 7 (n=5): predose Day 2, +3h, +7h SubGroup 8 (n=5): predose Day 2, +2h, +48h SubGroup 9 (n=5): predose Day 2, +5h, +7h SubGroup 10 (n=5): predose Day 2, +1h, +24h

Global Health

Sensitivity analysis populations

ISGIODAI Barcelona Institute for

Safety sensitive populations: A per-protocol analysis will be performed including all randomized participants who received at least one dose of medication.

Efficacy sensitive population: A per-protocol analysis will be conducted, including all randomized participants who received at least one dose of medication, did not withdraw, without major protocol deviations, and were not lost to follow-up. Also, participants who did not meet the inclusion or exclusion criteria, received an incorrect treatment, or were administered an incorrect dose will be excluded from the per-protocol analysis.

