5.4.4 Multiplicity

Multiplicity adjustment will not apply to the primary and secondary outcome analyses.

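### Stated power does not match the planned analysis: counting missing Day-21 results as failures lowers FDC vs FDCx3 from 80% to about 75% (T. trichiura), 55% (S. stercoralis) and 53% (hookworm) at alpha 0.0167; the primary comparisons with ALB hold

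*SAP*

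**What the plan says.** **Analysis rule.** SAP 4.1 bases efficacy on the ITT population, "considering all individuals without efficacy data as treatment failures". SAP 5.1.5 repeats the rule: "the worst-case scenario will be considered, where participants with missing data will be considered as treatment failures". SAP 5.4 makes ITT the basis of the primary efficacy analysis and applies the same cure-rate approach to hookworm and S. stercoralis (5.4.1).

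**Sizing.** SAP 3.5 and protocol 9.2 describe pairwise comparisons with Bonferroni correction, "80% power and inflated for 10% lost-to-follow-up". For T. trichiura, "The corresponding powers of each of the tests are 91%, 100% and 80" per cent for ALB vs FDC, ALB vs FDCx3 and FDC vs FDCx3 in turn. Table 3 of the SAP (Table 1 of the protocol) gives 80% for FDC vs FDCx3 in all three species and 82% for hookworm ALB vs FDCx3. The footnote to the final sample-size table (protocol Table 2, SAP Table 4) reads "Calculated by inflating the sample size using considering 10% lost-to-follow-up".

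**Alpha.** The power table uses 0.0167 per comparison. SAP 5.4.4 says "Multiplicity adjustment will not apply to the primary and secondary outcome analyses".

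**Sensitivity analysis.** Protocol 9.5.8 allows multiple imputation if it proves necessary. SAP 5.1.5 uses imputation only for baseline age, gender, height and weight. The only efficacy sensitivity set is per-protocol, limited to participants who "did not withdraw, without major protocol deviations, and were not lost to follow-up".

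**The concern.** Dividing n by 0.9 is the right allowance when lost participants drop out of numerator and denominator alike. It is not the right allowance when they stay in the denominator as failures, because then the expected cure rates fall as well. The arm difference shrinks by a tenth. Where cure rates are high, the binomial variance also rises sharply: at 95% cure p(1−p) is 0.0475, while at 85.5% it is 0.124. The loss of power should therefore be small for T. trichiura and large for S. stercoralis and hookworm.

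Both documents say the trial is powered for all three species, and FDC vs FDCx3 is the comparison that sits at 80% in each of them. They also say that assumed cure rates and loss should be checked at the interim. If ITT cure rates with failures imputed were compared with Table 3, they would look about 10% (relative) low even if every planning assumption were correct.

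**Working it through.** **Inputs** (SAP 3.5, Tables 3 and 4; arms in the order ALB / FDC / FDCx3)

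| Species | Cure rates | Evaluable n | Randomised N |
|---|---|---|---|
| T. trichiura | 23.7 / 43.7 / 59% | 116 / 223 / 223 | 129 / 248 / 248 |
| S. stercoralis | 45 / 79 / 94% | 42 / 108 / 107 | 47 / 120 / 119 |
| Hookworm | 79.5 / 79.5 / 95% | 91 / 91 / 99 | 101 / 101 / 110 |

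Tests are two-sided (SAP 5.7), with alpha 0.05/3 = 0.0167 (z = 2.394). Results at 0.05 (z = 1.960) are also given because of SAP 5.4.4.

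**Formula** (pooled variance under the null, no continuity correction)

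power = Φ[(|p2 − p1| − z·s0) / s1], where s0 = √{p̄(1−p̄)(1/n1 + 1/n2)}, s1 = √{p1(1−p1)/n1 + p2(1−p2)/n2}, and p̄ is the n-weighted mean cure rate.

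**Step 1. Reproduce the stated power** (evaluable n, undiluted rates, alpha 0.0167)

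- T. trichiura FDC vs FDCx3: difference 0.153, s0 = 0.04733, s1 = 0.04678; Φ(0.848) = 80.2%.
- S. stercoralis FDC vs FDCx3: 80.0%. Hookworm FDC vs FDCx3: 80.1%.
- ALB vs FDC: 90.6% for T. trichiura (stated 91%) and 94.7% for S. stercoralis (stated 95%).
- Hookworm ALB vs FDCx3: 80.1% (stated 82%). About 2 points of that gap are therefore a discrepancy in the table itself.

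The method matches the plan's, and the randomised N equal n/0.9 after rounding.

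**Step 2. Apply the SAP's rule at 10% loss** (randomised N, each cure rate × 0.9)

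FDC vs FDCx3 rates become 39.3 vs 53.1%, 71.1 vs 84.6%, and 71.6 vs 85.5%.

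- T. trichiura: difference 0.1377, s0 = 0.04477, s1 = 0.04434; Φ(0.688) = 75.4%.
- S. stercoralis: difference 0.135, s0 = 0.05375, s1 = 0.05298; Φ(0.120) = 54.8%.
- Hookworm: difference 0.1395, s0 = 0.0563, s1 = 0.05606; Φ(0.084) = 53.3%.

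| Comparison | Stated | 0.0167 | 0.05 |
|---|---|---|---|
| T. trichiura FDC vs FDCx3 | 80% | 75.4% | 87.0% |
| S. stercoralis FDC vs FDCx3 | 80% | 54.8% | 71.2% |
| Hookworm FDC vs FDCx3 | 80% | 53.3% | 69.8% |
| Hookworm ALB vs FDCx3 | 82% | 53.3% | 69.8% |
| S. stercoralis ALB vs FDC | 95% | 90.1% | 95.8% |
| S. stercoralis ALB vs FDCx3 | 100% | 99.9% | 100% |
| T. trichiura ALB vs FDC (primary) | 91% | 88.7% | 95.3% |
| T. trichiura ALB vs FDCx3 (primary) | 100% | 100% | 100% |

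For reference, dropping the lost participants at alpha 0.05 gives about 90% for FDC vs FDCx3 in each species. Simulation of the pooled test at 10% loss (200,000 runs) gives 75.6 / 55.5 / 54.0% at 0.0167 and 87.5 / 72.2 / 71.0% at 0.05, in agreement with the formula.

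**Step 3. Range** (FDC vs FDCx3; T. trichiura / S. stercoralis / hookworm)

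- 5% loss: 80.3 / 68.8 / 67.9% at 0.0167; 90.2 / 82.5 / 81.7% at 0.05.
- Highest loss that keeps 80% power: 5.3 / 1.5 / 1.4% at 0.0167; 19 / 6.1 / 5.7% at 0.05.
- N multiplier for 80% at 10% loss: 1.10 / 1.65 / 1.70 at 0.0167. At 0.05, S. stercoralis needs 1.23 and hookworm 1.28.
- Interim spending would lower the final alpha slightly. The SAP gives no schedule; assuming 0.049 at the final look, power is 86.8 / 70.9 / 69.5%.

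**The case against.** The arithmetic is not in dispute. The case against rests on what it means.

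- **FDC vs FDCx3 is not a listed hypothesis.** The specific hypotheses in protocol 9.1 and SAP 5.3.1 compare arms 2 and 3 with arm 1. Of the five powered comparisons with ALB, four stay above 80% even at 10% loss and 0.0167. This stands. But the plan explicitly powers FDC vs FDCx3 at 80% and sets 15 points as the smallest gain that would make FDCx3 worth considering. Hookworm ALB vs FDCx3, which is within a listed secondary hypothesis, falls just as far.
- **The analysis alpha may be 0.05.** At that level T. trichiura FDC vs FDCx3 has 87% power and no shortfall. This stands for T. trichiura. It does not rescue the other two species at 10% loss.
- **Loss may be lower.** Follow-up is about a month, largely school-based, with home visits. At 5% loss and alpha 0.05 there is no shortfall. The size is therefore conditional on loss, but 10% is the plan's own figure.
- **The planning rates might already count missing as failure.** The documents do not say. If they did, the 0.9 factor would double-count. But dividing n by 0.9 only makes sense if the rates apply to participants with data. If they did not, Table 4 numbers with undiluted rates would give about 85% for FDC vs FDCx3 at 0.0167 in each species. Either way the table does not describe the planned analysis.
- **Co-infection adds numbers.** Protocol 4.2 says "A participant infected with a mixture of worms will be counted in the sample size for each worm", and the SAP also analyses phase II hookworm and S. stercoralis co-infections, for which Table 4 allows none. Actual N may exceed the table, but neither document quantifies the surplus.
- **The interim check** could look at evaluable cure rates and loss separately, which would be sound. The plan does not say how it will be done, so a misleading check is a risk and not a certainty.
- **Multiple imputation** of cure is partly a matter of preference, since the protocol makes it conditional and the SAP then sets a rule. That part is optional.

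**Conclusion.** The concern holds. The stated powers are those of an analysis that drops lost participants, and the SAP specifies one that counts them as failures. At the plan's own 10% loss, FDC vs FDCx3 is below 80% for S. stercoralis and hookworm at either alpha (55% and 53% at 0.0167; 71% and 70% at 0.05). For T. trichiura it is below 80% only at 0.0167 (75%). Hookworm ALB vs FDCx3 is 53% or 70%. The primary T. trichiura comparisons with ALB remain well powered.

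These figures rest on four assumptions: 10% loss, equal across arms; loss unrelated to cure; planning cure rates that apply to participants with data; and Table 4 numbers with no surplus from co-infection. This should be fixed because the documents claim a design property they do not have for two of three species. It does not threaten the primary endpoint or the validity of the failure rule.

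**What to change.** 1. In SAP 3.5 and Table 3, and protocol 9.2 and Table 1, restate power for the ITT analysis with missing counted as failure. Name each comparison, the loss assumption and the alpha that will be used, which first requires settling 0.0167 or 0.05. At 10% loss the entries are: FDC vs FDCx3 75 / 55 / 53% at 0.0167 or 87 / 71 / 70% at 0.05 (T. trichiura / S. stercoralis / hookworm); hookworm ALB vs FDCx3 53% or 70%; T. trichiura ALB vs FDC 89% or 95%. State that co-infection may raise the per-species numbers.
2. Optionally, align SAP 5.1.5 with protocol 9.5.8 by replacing the conditional wording with a pre-specified sensitivity analysis: multiple imputation of Day-21 cure status for each species, reported beside the per-protocol analysis. The failure rule can stay as primary.

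The cost is wording in two documents and, if item 2 is taken up, one extra analysis. No participants are added. The price is a less favourable stated power for the regimen comparison and for hookworm.
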